Eligible patients will receive a total of 6 ketamine infusions and 5 WET sessions. The primary outcome will be change in PTSD symptom severity assessed by the Clinician-Administered PTSD Scale for DSM-5 (CAPS-5) from baseline (before the first infusion) to 12 weeks from the start of WET. All participants will be assessed until week 12 following the start of WET. They will complete weekly assessments from baseline until 6 weeks from the start of WET, as well as assessments at 12 weeks from the start of WET. At other time points between 6 and 12 weeks, participants will be assessed weekly, or less frequently as tolerated. Although initial response to ketamine (PTSD and co-morbid depressive symptom improvement) will be assessed after the first four infusions (prior to starting WET), all participants will receive 6 infusions and 5 WET sessions regardless of their initial response to ketamine. Participants will be asked not to make any changes to any concomitant treatment (i.e., medication dosages, psychotherapy) during this period.

Thereafter, participants who remain improved at the 12-week time point (compared to baseline) will then receive additional monthly assessments up to 24 weeks or until loss of this improvement.

We will also evaluate whether extinction learning ability –assessed with a computerized extinction learning task– is associated with PTSD symptom improvement from baseline to 12 weeks from the start of WET. If demonstrated to result in significant and maintained PTSD symptom improvement, this novel combined treatment may represent a promising intervention for individuals with chronic PTSD, deserving further study.

Objectives:

Primary Objective: To evaluate the efficacy of adding WET to ketamine therapy in improving PTSD symptoms from baseline to 12 weeks from the start of WET, in individuals with chronic PTSD .

Secondary Objectives (exploratory): (1) To evaluate improvement in PTSD symptoms from baseline to 6 weeks, and on other measures from baseline to 6 weeks, and from baseline to 12 weeks; (2) To evaluate durability of PTSD symptom improvement beyond 12 weeks in patients who remain improved, up to 24 weeks; (3) To evaluate whether ketamine-induced change in extinction learning is associated with improvement in PTSD symptoms from baseline to 12 weeks from the start of WET.

Endpoints:

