3 OBJECTIVES AND ENDPOINTS

OBJECTIVES	ENDPOINTS	JUSTIFICATION FOR ENDPOINTS
Primary		
To evaluate the efficacy of adding WET to ketamine therapy in improving PTSD symptoms from baseline to 12 weeks from the start of WET, in individuals with chronic PTSD.	Change in PTSD symptom severity, as assessed with the Clinician-Administered PTSD Scale for DSM-5 (CAPS-5), between baseline and 12 weeks following the start of WET.	The CAPS-5 is the gold-standard outcome measure in clinical trials in patients with PTSD. Timing and duration of primary outcome assessment

OBJECTIVES	ENDPOINTS	JUSTIFICATION FOR ENDPOINTS
		were selected based on findings from prior WET and repeated ketamine studies.
Secondary (Exploratory)		
To evaluate longitudinal change in PTSD and depressive symptoms (and clinical global impression and psychosocial functioning) following administration of ketamine infusions and WET, as well as the relationship between change in PTSD and depressive symptoms. All participants will be followed for 12 weeks from the start of WET. To capture any ketamine-related rapid changes in PTSD and depressive symptoms	Change in PTSD symptom severity from baseline to 6 weeks, using the CAPS-5; change in PCL-5, MADRS, CGI, and SDS from baseline to 6 weeks, and from baseline to 12 weeks; in patients with maintained PTSD symptom improvement after 12 weeks, change in PTSD symptom severity from baseline to 16, 20, and 24 weeks.	The CAPS-5 is the gold-standard outcome measure, and the PCL-5 is a self-report measure commonly used in clinical trials for PTSD. The MADRS (depressive symptoms), CGI (clinical global impression), and SDS (psychosocial functioning) are commonly used as well.
	Change in IES-R and QIDS-SR, with 24-hour recall, from baseline to 24 hours after the first infusion, at each infusion day, and 24 hours after the fourth infusion.	These scales are commonly used in clinical trials, including in our 2 previous clinical trials of ketamine for PTSD to capture rapid symptom improvement.
To evaluate whether ketamine-induced change in extinction learning predicts PTSD symptom improvement from baseline to 12 weeks from start of WET.	Performance on Extinction Learning Task following ketamine infusions.	The computerized Extinction Learning Task is sensitive to PTSD. Assessment time point after four infusions (compared to baseline) allows for assessment of maximal change in extinction learning prior to adding WET to ketamine treatment.

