b. Administration of ketamine infusions: Eligible participants will receive a total of six infusions, administered over two consecutive weeks. At each infusion, they will receive 0.5 mg/kg of racemic ketamine hydrochloride, and total dose no higher than 60 mg per infusion (regardless of body weight). All infusion procedures and monitoring will take place at the Icahn School of Medicine at Mount Sinai (ISMMS) Psychiatry Infusion Suite or Clinical Research Unite (CRU) using the existing Standard Operating Procedures that are in place for the administration of ketamine in research studies.

c. Assessment of response to ketamine: Response to ketamine, assessed 24 hours after the fourth infusion, is defined as $\geq 30\%$ reduction in PTSD symptom severity on the CAPS-5, administered to the participant by a trained clinical rater, compared to baseline (prior to any infusions). This degree of improvement is commonly used in clinical trials in individuals with PTSD to represent clinically significant PTSD symptom improvement,⁶²⁻⁶⁴ and was also employed in our completed RCT of repeated ketamine for PTSD.⁸

d. WET Sessions:

WET consists of five sessions, with the first session lasting 1 hour and each subsequent session lasting approximately 40 minutes. The first session includes psychoeducation about common trauma reactions and the treatment rationale, presented by the therapist. The participant is then given general instructions for completing the trauma narratives and specific instructions for completing the first 30-minute narrative writing during that first WET session. All WET sessions begin with the therapist reading the specific writing instructions, clarifying any questions the participant might have, and leaving the instructions with the participant during the 30-minute writing session. Writing instructions begin with a focus on the details of the trauma and then shift to the meaning of the trauma event. After 30 minutes of writing, the therapist stops the writing and conducts a 5-10 minute check-in regarding how the writing session went for the participant.

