Secondary outcome measures (exploratory): The CAPS-5 will be administered weekly (beginning at baseline prior to the first ketamine infusion) until 6 weeks from the start of WET; thereafter, the CAPS-5 will be administered weekly as tolerated until 12 weeks; all participants will be administered the CAPS-5 at the 12-week time point. Participants who maintain PTSD symptom improvement after 12 weeks will be assessed monthly up to 24 weeks from the start of WET or until loss of improvement, by the blinded clinical rater. The PCL-5 and SDS (self-report scales), the MADRS (administered by the blinded clinical rater), and the CGI-S and CGI-Improvement scales (administered by a study psychiatrist or clinician) will be administered at the same time points until 12 weeks, and then monthly up to 24 weeks or until loss of improvement (See **3.1 Schedule of Activities**). The Quick Inventory of Depressive Symptomatology-Self-Report version (QIDS-SR)⁶⁶ and the Impact of Events Scale-Revised (IES-R),⁶⁷ both self-report scales, will be administered at baseline, 24 hours after the first infusion, at each infusion visit, and on the day of response to ketamine assessment, to capture any ketamine-related rapid changes in symptom levels. An abbreviated version of the Medical Outcomes Study Social Support Survey (MOS-SSS),⁶⁸ the Centrality of Event Scale (CES),⁶⁹ and the Perceived Ability to Cope with Trauma Scale (PACT)⁷⁰ will be administered at baseline (prior to any infusions) and again 3 weeks after the first WET session; data from these scales will be used for Aim-3 analyses.

Safety Assessments: Participants will be evaluated prior to each infusion by the PI or another study-affiliated psychiatrist; including review of vital signs, weight/BMI, drug and pregnancy tests, concomitant medications and adverse events. Participants will be monitored continuously during all ketamine infusions. On infusion days, side effects will be assessed with the Patient-Rated Inventory of Side Effects (PRISE) Adverse Event Visit Checklist,⁷¹ the Clinician-Administered Dissociative States Scale (CADSS),⁷² the Brief Psychiatric Rating Scale (BPRS) 4 items assessing positive symptoms,⁷³ and the Young Mania Rating Scale first item.⁷⁴

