9.4.3 ANALYSIS OF THE SECONDARY ENDPOINT(S)

- **Secondary Efficacy Outcomes (Exploratory):** In this early-phase study, analyses of secondary efficacy outcomes will be considered exploratory and hypothesis-generating. CAPS-5, PCL-5, MADRS, CGI and SDS scores will be collected weekly through 6 weeks after the start of WET from all

eligible participants, and thereafter until 12 weeks (up to weekly, as tolerated, ensuring assessment at the 12-week time point for all participants). All participants will be followed naturally for 12 weeks from the start of WET, in order to capture, descriptively, more gradual effects of WET and potential effects of the combination of ketamine + WET in all patients. Thereafter, they will be collected monthly through week 24 from start of WET or until loss of treatment response, for the subgroup of participants who demonstrate improvement on the CAPS-5 at the 12-week assessment. Aggregate scores prior to adding WET, during WET, and during the maintenance phase (weeks 3 onward) will be reported descriptively at each time point using the number observed, mean, standard deviation, median, and interquartile range. Individual patient trajectories on these measures will be plotted over time to explore treatment response and patterns in maintenance of response. Mean change in CAPS-5 scores from baseline and corresponding 95% confidence intervals, as well as the proportion of patients with $\geq 30\%$ improvement from baseline on the CAPS-5 will also be reported at each time point. In addition, linear mixed-effects models of these outcomes may be fit to compare mean scores over time. Mixed models will test for the inclusion of a random intercept for patient and fixed effects for week against a fixed intercept model using a likelihood ratio test after comparing each model fit statistic (i.e., Akaike information criterion, AIC) where the best fitting model is the model with the lowest corresponding AIC. Once fit is assessed, parameter interpretation will commence.

- **IES-R and QIDS-SR with past-24-hour recall** – collected only at baseline, before each ketamine infusion, 24 hours after the first infusion, and on the response to ketamine assessment day – will be examined descriptively.

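### After week 12 the CAPS-5 is collected only until improvement is lost, so observed-case results at weeks 20 and 24 lean high as a measure of durability, and the denominator of the 30% proportion is not stated

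*Combined protocol and SAP*

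**What the plan says.** The second secondary objective in Section 1.1 is "To evaluate durability of PTSD symptom improvement beyond 12 weeks in patients who remain improved, up to 24 weeks". The matching endpoint in Section 3 is, "in patients with maintained PTSD symptom improvement after 12 weeks, change in PTSD symptom severity from baseline to 16, 20, and 24 weeks".

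Collection after week 12 is restricted in several places:
- Section 1.1: those still improved at week 12 "will then receive additional monthly assessments up to 24 weeks or until loss of this improvement".
- Section 4.1: they "will be assessed monthly up to 24 weeks from the start of WET or until loss of improvement".
- Section 9.4.3, judging improvement by the week-12 CAPS-5: "monthly through week 24 from start of WET or until loss of treatment response, for the subgroup of participants who demonstrate improvement".
- Section 4.4 ties the end of study to loss of this improvement, and Section 8.1 ends several scales at loss of response.

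Section 9.4.3 has scores "reported descriptively at each time point using the number observed, mean, standard deviation, median, and interquartile range". It adds mean CAPS-5 change with 95% intervals and the proportion with at least 30% "improvement from baseline on the CAPS-5 will also be reported at each time point". No denominator is given. Section 9.4.1 asks for the number of non-missing values with counts and percentages, and Section 9.3 defines a set of all enrolled patients. Neither is tied to this proportion.

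The only response defined by a number concerns an earlier visit: "Response to ketamine, assessed 24 hours after the fourth infusion, is defined as" a CAPS-5 reduction of at least 30% (Section 4.1, repeated in 6.1.2). Section 9.4.1 names Kaplan-Meier and patient-time event rates in general terms, without linking either to loss of improvement.

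**The concern.** The outcome itself ends its own measurement. A participant who loses improvement at week 16 contributes nothing at weeks 20 or 24, while one who keeps it stays in the summary. An observed-case mean or percentage at those visits therefore describes survivors of the exit rule, and it can look stable while week-12 improvers relapse.

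Durability is the motive for the trial. Section 1.1 cites a median of 27.5 days to loss of response after ketamine alone, and Section 9.4.3 leaves room for a comparison with that earlier study. A flat or rising percentage after week 12 could be taken as evidence that adding WET maintains the gain.

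**Working it through.** **The plan's own figures.** The documents give no expected value for any result after week 12. The precision statement in Section 9.2 (half-width 0.5 SD with 15 patients; 1.96/√15 = 0.506) concerns the week-12 mean and does not bear on this point.

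**Step 1: who is observed.** Week 16: all week-12 improvers are due. Week 20: those not lost at week 16. Week 24: those not lost at week 16 or 20. A line drawn from week 12 to week 16 also changes base, from all participants to improvers only.

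**Step 2: direction.** Let q be the chance of loss between monthly visits (assumed), with exit at loss and no regain. The observed-case proportion is 1 − q at every visit. Among all week-12 improvers it is (1 − q), (1 − q)², (1 − q)³.
- q = 10%: observed 90% throughout; all improvers 90, 81, 73%.
- q = 20%: observed 80% throughout; all improvers 80, 64, 51%.
- q = 30%: observed 70% throughout; all improvers 70, 49, 34%.

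If lost improvement is regained with monthly chance r, the week-20 gap is (1 − q) − [(1 − q)² + qr] = q(1 − q − r), which is upward whenever r < 1 − q. For q = 20% and r = 30% it is 0.2 × 0.5 = 10 points (80% against 70%). Forbidding regain makes the gap large, so this step shows direction only.

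**Step 3: size if changes persist (random walk).** All inputs are assumed: week-12 percent improvement normal with mean 45 and SD 25, capped at 100; baseline CAPS-5 of 40; every 4 weeks an average loss of 5 or 10 percentage points plus noise of SD 15; exit after the first visit below the cut; no other dropout. The 30% cut is one plausible case because it is the only response cut defined in the main text. Week-24 results, with the last column counting exits as not improved over all week-12 improvers:

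| Exit cut | Loss per 4 weeks | Still assessed | ≥30%, observed | ≥30%, all improvers | Gap | Mean change, observed vs all | Fixed denominator, error |
|---|---|---|---|---|---|---|---|
| Any improvement | 5 | 87.0% | 59.4% | 51.8% | +7.6 | −15.4 vs −12.6 | 0 |
| Any improvement | 10 | 79.3% | 44.2% | 35.1% | +9.1 | −11.1 vs −6.7 | 0 |
| 30% | 5 | 68.2% | 84.2% | 63.3% | +20.9 | −21.7 vs −16.3 | about −6 |
| 30% | 10 | 55.2% | 73.1% | 44.5% | +28.6 | −18.1 vs −10.4 | about −4 |

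At week 20 the gaps are +3.6 and +4.3 points (any improvement) and +11.7 and +15.9 (30%). At week 16 they are zero. With a 30% exit and a loss of 5, the observed-case series over weeks 16, 20 and 24 is 82, 83, 84%, while the series for all improvers is 82, 72, 63%.

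Per 10 improvers, the week-24 gap is 0.8 to 0.9 of a person (any improvement) or 2.1 to 2.9 people (30%). Varying the week-12 mean (35, 45, 55), noise SD (10, 15, 20) and loss (0, 5, 10) gives 27 scenarios per cut. The week-24 gap runs from 1.8 to 14.0 points (any improvement) and from 6.3 to 31.9 points (30%).

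**Step 4: size if scores fluctuate around a personal level.** Same mean 45 and total SD 25, but noise independent at each visit. Week 24, 30% exit, observed-case gap against fixed-denominator error (points):

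| Noise SD | Loss 0 | Loss 5 | Loss 10 |
|---|---|---|---|
| 15 | +7.0 / −16.2 | +15.0 / −15.1 | +21.0 / −10.1 |
| 20 | +6.3 / −23.8 | +11.3 / −22.3 | +14.2 / −15.7 |

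Observed-case figures still lean high. In five of the six cases, however, the fixed-denominator figure is at least as far from the truth, on the low side, because participants who dip once and recover are never seen again. With the any-improvement exit and noise SD 15, the observed-case gap is +2.5 to +5.2.

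**The case against.** The strongest reply is that the plan declares a conditional quantity. Sections 1.1 and 3 limit the later endpoints to participants with maintained improvement. If that means still improved at each visit, observed-case means are what was declared. This stands, but those figures then do not say how many improvers were lost, which is what durability asks.

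Second, much is disclosed. The number observed is reported and individual trajectories are plotted, so with at most 15 enrolled a reader could largely recover the losses. Kaplan-Meier is already named, and Section 4.4 mentions time to loss. This also stands in part: the remedy is largely a missing link. Disclosure does not change the printed means and percentages, though. The mixed models could help with means, since exit depends on an observed score, but they are optional and do not supply the proportion.

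Third, the stakes are small. The analyses are exploratory and untested, and sampling error is far larger: 6 of 10 has an exact 95% interval of 26% to 88%. This is accepted, and it limits the priority of the point.

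A reader might infer that the fixed-denominator proportion is the correct answer and should replace the observed one. Step 4 shows otherwise. It came closer to the truth in all 54 random-walk scenarios, but that result belongs to the random walk, and the documents do not favour that model over fluctuating scores.

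**Conclusion.** The point holds as a reporting gap in an exploratory secondary objective. As a measure of durability among week-12 improvers, observed-case figures lean high at weeks 20 and 24 and not at week 16. The direction follows from the collection rule unless regain is very frequent (r at or above 1 − q in the simple model). The size is uncertain: in the random-walk scenarios, roughly 2 to 14 points at week 24 with an any-improvement exit and roughly 6 to 32 with a 30% exit, all on assumed inputs and an unstated cut.

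Stronger readings are not supported. The plan does not commit to an observed-case denominator; it leaves the denominator open. A gap of 20 points or more should not be presented as expected, since it needs a 30% exit that the current text does not state. The week-12 primary endpoint is untouched, and no formal test is involved.

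**What to change.** 1. Reconcile the four wordings of the exit rule (Sections 1.1 and 4.4; 4.1; 8.1; 9.4.3) and state one definition of loss for the analysis. Which cut to use is for the study team.
2. Make the Kaplan-Meier method already named in Section 9.4.1 the main durability summary: time from week 12 to first documented loss, with other dropouts and week-24 completers censored.
3. At weeks 16, 20 and 24 report the 30% proportion over those observed, with n, and also over all week-12 improvers and over all enrolled. For the last two, count documented losses as not improved and show other dropouts as a separate category. Describe the all-improvers figure as a lower bound and the observed-case figure as leaning high; neither corrects the other.
4. Label mean changes at weeks 20 and 24 as conditional on still being followed, with n.

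The cost is a few SAP definitions and slightly more analysis, with no new data and no endpoint removed. Durability will look less favourable. Because regain after exit is unseen, the lower bound can itself be too low at week 24 with a 30% exit: by about 4 to 6 points in the main random-walk cases, and by about 10 to 24 points if scores fluctuate around a personal level. The text should say so.

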For Aim 2, extinction learning will be measured twice, with two versions of the online Extinction Learning Task: (1) before the first ketamine infusion and (2) after completion of four ketamine infusions (pre-WET). Extinction learning will be defined as the difference in discrimination between the aversively conditioned (CS+) and safe (CS-) stimuli on the first six blocks of this task. Ketamine-induced change in extinction learning will be evaluated as a predictor PTSD symptom improvement from baseline to 12 weeks from the start of WET. A recently developed computational model^{75,76} will be employed to determine whether differences in discrimination between CS+ and CS- are related to differential inferences about the causal structure of the task during learning (i.e., participants' belief that one vs. multiple underlying causes explain observations during progression through the task).⁴⁸

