extinction learning (in novel context B) (see Figure 7). Importantly, the conditioned stimulus (CS) associated with the aversive loss outcome (US), the CS+, is only partially reinforced ($P(US|CS+)=1/3$), and the transition to extinction ($P(US|CS+)=0$) is unsignaled. This design maximizes uncertainty about whether CS+ trials during extinction should be grouped with unreinforced conditioning phase CS+ trials, implying a common cause is responsible for both kinds of observations, or instead that the change in contingencies indicates it is likely that a new cause is active in the environment. The predictive measure generated from this task for Aim 2 analyses (PTSD symptom change between baseline and 12 weeks from the start of WET) is the difference in discrimination between CS+ and CS- across the first six blocks of the task.

Further, loss expectancy ratings data from each trial of the online extinction task will be analyzed via a computational model of latent cause inference developed by Gershman, Niv, and colleagues^{75,76} (see Data Analysis Strategy). There are two versions of the task (see description in Figure 7 note): one version will be administered prior to any ketamine infusions, and the second version after completion of the first four infusions. We will examine whether improvement in extinction learning from baseline to completion of four initial ketamine infusions (prior to starting WET) is associated with PTSD symptom improvement from baseline to 12 weeks from the start of WET.

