9.2 SAMPLE SIZE DETERMINATION

In this pilot study up to 15 patients will be enrolled. A sample size of 15 patients will produce a two-sided 95% confidence interval around the mean change in CAPS-5 at 12 weeks from the start of WET with a distance from the mean to the limits that is equal to 0.5 standard deviations.

Precision was calculated using PASS 2019.⁸³

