The relationship between depressive symptoms and PTSD will be explored to assess whether worsening depressive symptoms correlate with worsening PTSD symptoms and whether there is any evidence that the worsening of one precedes the other. Scale scores of both measures will be plotted over time together to evaluate trends descriptively. Fixed and mixed effects regression models will also be explored to estimate effects and 95% confidence intervals.

- Finally, additional analyses might explore differences with a historical comparison group from our published repeated IV ketamine study for PTSD (Feder et al 2021).

Aim 2 (Exploratory): To evaluate whether ketamine-induced change in extinction learning predicts maintenance of ketamine response over time. We will use regression models to evaluate whether ketamine-induced change in extinction learning [improvement in extinction learning between two time points: (1) before infusions and (2) after four infusions (prior to starting WET), measured with the computerized online Extinction Learning Task, is associated with change in CAPS-5 at 12 weeks after the start of WET. A univariable model of ketamine-induced change on the extinction learning measure [discrimination between aversively conditioned (CS+) and safe (CS-) stimuli over the first six blocks of the task] and changes in CAPS-5 score will be examined. Beta coefficients and 95% confidence intervals will be reported. A significant association between greater ketamine-induced improvement in extinction learning and improvement in CAPS-5 scores will be considered supportive of Hypothesis 2.

Computational analyses: Loss expectancy ratings data from each trial of the online extinction task will be analyzed via a computational model of latent cause inference developed by Gershman, Niv, and colleagues.^{75,76} Importantly, this model has previously been shown to be able to explain individual differences in failure of extinction learning in both healthy volunteers and trauma-exposed individuals

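### Aim 2 asks about maintenance of ketamine response, but its outcome includes the early CAPS-5 change already complete when the predictor is measured, and the model does not adjust for it

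*Combined protocol and SAP*

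**What the plan says.** **The question.** The Aim 2 paragraph of Section 9.4.3 opens: "To evaluate whether ketamine-induced change in extinction learning predicts maintenance of ketamine response over time". It goes on to say that a significant association in the expected direction will be taken as support for Hypothesis 2, which Section 9.1 does not set out.

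**The predictor.** It is the change in CS+/CS- discrimination between a first task before any infusion and a second task after four infusions. The Schedule of Activities (Section 1.3) puts the first task in the screening column (Day -28 to 0) and the second on Day 9. CAPS-5 is scheduled on Day 1 and again on Day 9.

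**The outcome.** Section 4.2 says: "Ketamine-induced change in extinction learning will be evaluated as a predictor PTSD symptom improvement from baseline to 12 weeks from the start of WET". Section 8.1 asks whether the task improvement "is associated with PTSD symptom improvement from baseline to 12 weeks from the start of WET", and Sections 1.1, 3 and 4.1 agree. Section 9.4.3 asks only whether task change "is associated with change in CAPS-5 at 12 weeks after the start of WET" and gives no point from which the change is counted.

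**A competing rule.** Section 9.4.1 defines change, for any repeatedly measured variable, from the pre-WET day on which response to ketamine is assessed (Day 9). Sections 9.4.2 and 9.4.3 nevertheless use baseline for the other CAPS-5 change analyses.

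**The model.** It is "A univariable model of ketamine-induced change on the extinction learning measure" and CAPS-5 change. No CAPS-5 score enters as a covariate.

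**The concern.** CAPS-5 change from baseline to week 12 is the Day 1–9 change plus the Day 9-to-week-12 change. The first part is finished when the second task is taken, and only the second part bears on maintenance. If four infusions lower symptoms and shift task ratings in the same people, the univariable slope picks that up even when task change carries no information about what follows.

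At stake is the reading of the result. A concurrent effect of ketamine on two measures could be reported as evidence that improved extinction learning sustains the benefit. That is the mechanism the protocol proposes for adding WET, and it could shape a follow-on trial.

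**Working it through.** **The plan's own figure.** Section 9.2 states: "In this pilot study up to 15 patients will be enrolled". It gives a 95% interval "with a distance from the mean to the limits that is equal to 0.5 standard deviations". This reproduces with a known SD: 1.96/√15 = 0.506 SD (the t-based value is 0.554 SD). It concerns mean CAPS-5 change. No precision is given for Aim 2, so the figure neither supports nor weakens this point.

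**Timeline (Section 1.3).** CAPS-5 baseline is Day 1, the second task and CAPS-5 are on Day 9, and WET starts on Day 10. Week 12 is then about Day 10 + 84 = Day 94. The predictor window opens at screening, not Day 1, but contains all of Day 1–9.

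**Set-up.** Let B be baseline CAPS-5, C1 the Day 1–9 change, X the task change (signs aligned), k the share of C1 still present at week 12, and e later variation unrelated to X. Then Day-9 score = B + C1 and week-12 score = B + k·C1 + e.

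- Planned outcome: week 12 − B = k·C1 + e. Its slope on X is k times the concurrent slope, so at k = 1 the concurrent slope passes through in full.
- With ρ = corr(X, C1) and q = SD(e)/SD(C1), the expected correlation is kρ/√(k² + q²). At k = 1, ρ = 0.5, q = 1 this is 0.5/√2 = 0.354.

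**Assumed inputs.** The documents give neither ρ nor q. I took ρ = 0.3, 0.5, 0.7 and q = 1.0 and 0.5. For k I took 1, 0.5 and 0.14. The last assumes exponential fading with the 27.5-day median time to loss of response in Section 4.2 used as a half-life, from about Day 15 to Day 94: 0.5^(79/27.5) = 0.137. Two-sided 0.05 is assumed, because 9.4.3 states no level.

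**Share of simulated trials (n = 15) in which the planned model is significant although X is unrelated to later change given C1** (q = 1.0 / q = 0.5):

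| ρ | k = 1 | k = 0.5 | k = 0.14 |
|---|---|---|---|
| 0.3 | 12% / 16% | 8% / 11% | 5% / 6% |
| 0.5 | 26% / 40% | 13% / 26% | 6% / 8% |
| 0.7 | 49% / 75% | 21% / 49% | 6% / 10% |

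On the CAPS-5 scale, with an early-change SD of 10.5 and a later-change SD of 10 or 5, the ranges are 12–77%, 8–51% and 6–10%. The 10.5 is borrowed from Section 4.2 (11.88/1.13 = 10.5). It underlies a between-group effect at week 2 after six infusions, so it only approximates the within-person Day 1–9 SD.

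**Alternatives, same scenarios.**

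- *Simple Day-9-to-week-12 change* equals (k − 1)·C1 + e. It gives 5% at k = 1. At k = 0.5 it gives an association of the opposite sign (standardised slope −0.25 at ρ = 0.5) and rejects in 8–49%.
- *Week-12 score adjusted for Day 9 only.* The week-12 score equals k·(Day 9) + (1 − k)·B + e. At a given Day-9 score, B is still related to X through C1, so bias remains unless k = 1. Rejection is about 5% at k = 1, 5–16% at k = 0.5 and 6–27% at k = 0.14.
- *Adjusted for baseline and Day 9.* By the same identity nothing is left for X. Rejection is about 5% in every scenario (assumed baseline SD 8).

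**The case against.** - **Section 9.4.1 would remove the overlap.** Read literally, its pre-WET rule starts the Aim 2 outcome at Day 9. This stands in part: a reader might infer that the overlap is unavoidable as written, and the documents do not settle that. But 9.4.1 conflicts with Sections 4.2 and 8.1, 9.4.3 does not choose between them, and the simple change score it implies is biased if the early gain fades.
- **Total improvement is a legitimate target.** Sections 1.1 and 3 ask about improvement from baseline to week 12. For that question the correlation in these scenarios is truly non-zero, so detecting it is no error. If extinction change itself drives early relief, adjustment also removes part of the effect of interest. This stands. A reader might infer that the percentages above are false-positive rates for Aim 2 in general. They are errors only for the maintenance question posed in 9.4.3.
- **Ketamine gains fade.** The earlier trial's 27.5-day median suggests little of the early gain may remain at week 12, and then the planned model rejects in at most about 10%. This stands as a limit on size. WET is added to prevent that fading, however, so the problem grows as the treatment succeeds.
- **The analysis is exploratory.** Section 9.1 plans no formal testing of secondary outcomes, and 9.4.3 reports coefficients with intervals and also uses the language of association. This limits the consequence, but 9.4.3 still names a significant association as support for its hypothesis.

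**Conclusion.** The point holds as a mismatch between the question asked in 9.4.3 and the outcome and model used to answer it, together with an unresolved starting point between 9.4.1 and Sections 4.2 and 8.1. An association confined to the early symptom fall could be read as support for maintenance. Its likelihood runs from about 12–77% of trials if the early gain is fully kept, through 8–51% if half fades, to 6–10% if about 14% remains. These figures rest on assumed concurrent correlations of 0.3–0.7, assumed SDs and 15 complete participants. The upper end is the no-fading extreme and should not be quoted alone. The overlap itself follows from the documents wherever baseline is the starting point. The matter is worth correcting because the needed scores are already scheduled, but it does not touch the primary analysis.

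**What to change.** In Section 9.4.3:

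1. State the starting point of the Aim 2 CAPS-5 change, and reconcile the general rule in 9.4.1 with Sections 4.2 and 8.1.
2. For the maintenance question, regress week-12 CAPS-5 on task change with both baseline and Day-9 (pre-WET) CAPS-5 as covariates. Report the slope and 95% confidence interval.
3. Keep the univariable baseline-to-week-12 model, described as association with total improvement only.
4. Report the association between task change and CAPS-5 change up to Day 9 separately, labelled concurrent.

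Neither a simple Day-9-to-week-12 change nor adjustment for Day 9 alone should replace step 2, since both mislead if the early gain fades.

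The cost is SAP wording and two residual degrees of freedom (from 15 − 2 = 13 to 15 − 4 = 11). No new data are needed. The adjusted slope will be imprecise at n = 15, and the report should say so.
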